4.2 Study Duration

Subjects enrolled in this trial will be asked to participate for approximately 4 months and will complete 4 visits: 1 screening visit, 1 RF treatment visit, and 2 follow-up visits at 8 weeks (\pm 2 weeks) and 12 weeks (\pm 2 weeks) post-treatment.

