4.3.2 Safety Assessments

4.3.2.1 *Incidence and Severity of Adverse Events:*

Following the first RF treatment, adverse device effects (ADEs) will be assessed post-treatment and at each subsequent subject visit using the following scale:

- 1= mild: requires minimal or no treatment and does not interfere with the Subject's daily activities.
- 2= moderate: may cause some interference with functioning.
- 3= severe: interrupts Subject's usual daily activity and may require treatment.

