7.2 Recording Adverse Device Effects

All potential ADEs will be evaluated and must be recorded in the subject's medical chart and in the study case report forms. ADEs will be monitored and tracked from the time of the first RF treatment.

At each contact with the subject, the Investigator will seek information on ADEs by specific questioning and, as appropriate, by examination. ADEs may be observed by the Investigator and/or clinical research staff, elicited from the subject and/or family member or volunteered by the subject. All observed and volunteered adverse signs and symptoms (both expected and unexpected), regardless of severity or frequency, will be recorded in the case histories (medical chart and CRFs). Included in the description should be the nature of the sign or symptom, the date of onset, date of resolution (duration), the severity, whether the event was expected or unexpected (anticipated or unanticipated), the relationship to study treatment or other therapy, the action taken (if any), and the outcome.

All SADEs and UADEs must be reported according to Cutera and IRB requirements.

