7.3 Follow-up of Subjects after ADEs

All reported ADEs should be followed until resolution or until the subject's participation in the study ends. Resolutions of such events are to be documented on the appropriate CRF pages. All ADEs that result in permanent discontinuation from this clinical trial, whether serious or not, will also be reported on the Subject Non-Completion of Study Form.

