9.2 Analysis Sets

The efficacy analysis set will include all enrolled subjects who complete the RF treatment session using the study device.

The safety analysis set will include all subjects enrolled in the study who start the RF treatment session using the study device.

Missing data will not be imputed for efficacy or safety endpoints.

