9.4 Safety Analyses

Device-related and procedure-related adverse effects (AEs) and subjects who prematurely terminate from the study due to an adverse device effect, [REDACTED] will be tabulated and analyzed. For a given AE term, counting will be done by subject, not by event, i.e. for a subject reporting the same AE more than once, the event will be counted only once, at the most severe and longest duration. The number and percentage of subjects experiencing each AE Term will be descriptively summarized. [REDACTED]

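### Does the once-per-subject rule in section 9.4 leave adverse effect results undefined when the worst episode is not the longest, or when an effect is still open at the last visit?

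*Combined protocol and SAP*

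**What the plan says.** The safety endpoint in section 4.1.2 has two components, incidence and severity of adverse device effects. Duration is not one of them. Severity is graded on three levels in section 4.3.2; the middle one reads "2= moderate: may cause some interference with functioning".

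Section 9.4 counts by subject within each term. For a subject who reports the same term more than once, "the event will be counted only once, at the most severe and longest duration". The visible output is stated next: "The number and percentage of subjects experiencing each AE Term will be descriptively summarized". The section is redacted inside its first sentence and again straight after this one.

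The source data are set out elsewhere. Section 6.4 has severity and duration recorded at each follow-up visit. Section 7.2 requires, for each sign or symptom, "the date of onset, date of resolution (duration), the severity", and further on "the action taken (if any), and the outcome". Section 7.3 sets the end of observation: "All reported ADEs should be followed until resolution or until the subject's participation in the study ends". Section 9.2 adds: "Missing data will not be imputed for efficacy or safety endpoints". Section 4.2 plans "1 screening visit, 1 RF treatment visit, and 2 follow-up visits at 8 weeks" and at 12 weeks, each within 2 weeks either way.

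**The concern.** The phrase in section 9.4 attaches two attributes to one count. If a subject's worst episode is not the longest, no single episode has both. One analyst could take the two maxima separately, and another could pick one episode and report its severity and duration together. The same records would then give different descriptions of that subject.

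The second worry is about effects that never resolve within the study. Section 7.3 stops follow-up when participation ends, so an effect can be left with no resolution date and hence no complete duration. The visible text of section 9.4 does not say whether such an effect is shown as ongoing, given a minimum duration, or left out. Leaving it out would understate exactly the longest-lasting effects, which would be unwelcome in a device safety summary.

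**Working it through.** **1. Which results depend on the rule.** Take an assumed subject with two episodes of one term: grade 3 for 4 days and grade 1 for 30 days.

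| Reading | Subjects counted | Severity | Duration |
|---|---|---|---|
| Separate maxima | 1 | 3 | 30 days |
| Most severe episode | 1 | 3 | 4 days |
| Longest episode | 1 | 1 | 30 days |

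The count is 1 in every row, or 1/40 = 2.5% if all 40 subjects permitted by section 9.1 are treated. Only the third reading changes severity, and it is not a tenable one, because it ignores the instruction to take the most severe. Under the two tenable readings both components of the endpoint are identical and only duration moves.

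**2. Which reading is natural.** The rule names two superlatives for one subject and one term. Taking each over all of that subject's episodes satisfies both, always gives an answer and needs no tie-break. Choosing a single episode fails whenever the two superlatives point to different episodes.

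**3. Open effects.** For a subject who completes the study, the last visit falls between (12 − 2) × 7 = 70 and (12 + 2) × 7 = 98 days after treatment; withdrawal under section 5.3 can end observation sooner. Suppose an effect starts on day 0 and is still open at a visit on day 84 (12 × 7). The record then holds an onset date, no resolution date, and an outcome. These identify the effect as ongoing for at least 84 days. The subject is counted and the worst grade is known.

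**4. How often the pairing could matter.** The documents give no repeat rate, grade distribution or severity–duration correlation, so all three are assumed. For two independent episodes, with bivariate normal severity and duration and severity cut into three grades, simulation of 4,000,000 pairs gives:

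| Grade split | P(grades tie) | Correlation | P(longest is not worst, given grades differ) | Including ties |
|---|---|---|---|---|
| Equal | 0.333 | 0 | 0.500 | 0.333 |
| Equal | 0.333 | 0.5 | 0.288 | 0.192 |
| Equal | 0.333 | 0.8 | 0.136 | 0.091 |
| 80/15/5 | 0.665 | 0 | 0.500 | 0.168 |
| 80/15/5 | 0.665 | 0.5 | 0.257 | 0.086 |
| 80/15/5 | 0.665 | 0.8 | 0.105 | 0.035 |

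The tie probabilities are 3 × (1/3)² = 0.333 and 0.80² + 0.15² + 0.05² = 0.665. The last column is (1 − tie probability) × the column before it, for example (1 − 0.333) × 0.288 = 0.192.

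- If 2 to 10 subjects have two episodes of one term at different grades, the number affected runs from 2 × 0.105 = 0.2 to 10 × 0.500 = 5.
- If the 2 to 10 are all subjects with any repeat, it runs from 2 × 0.035 = 0.07 to 10 × 0.333 = 3.3.

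The full span, 0.07 to 5 subjects, is about 70-fold (5/0.07 ≈ 71). It describes the assumptions more than this trial. With one treatment and two follow-up visits, nothing visible suggests that repeats of one term will be common. The figures also bear only on the pairing of duration with severity; the change in subject counts and maximum severity stays at zero throughout.

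**The case for a change.** The best argument for raising the point is that the sponsor collects duration, records it for every effect and names it in the counting rule, so the rule ought to return one value from one set of records. The open-effect half is the stronger one. Section 7.3 itself foresees effects without a resolution date. The ban on imputation in section 9.2 covers endpoints, which duration is not, and even if it reached duration it would not say how to display an open effect. If open episodes were dropped, a subject with one effect open from day 0 to day 84 and another that resolved in 5 days would show a longest duration of 5 days.

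Part of this stands. The visible wording would be tighter with one more sentence, and nothing visible expressly rules out dropping an open episode. But doing so means setting aside a recorded, identifiable ongoing effect when asked for the longest, which is not a fair application of the rule. The harm also needs a duration summary, and none is visible. If one is planned, it is in redacted text that may equally hold the convention, and text lost to redaction cannot be counted as absent from the plan.

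**Conclusion.** The concern does not hold. Applied as written, section 9.4 gives a sound count of subjects per term and a sound maximum severity, which together are the declared safety endpoint; the effect of the ambiguity on both is zero. The phrase reads naturally as two separate maxima, and open effects can be identified from data the plan already collects. In a feasibility study of up to 40 subjects with no formal testing (sections 9.1 and 9.3.1), what remains is an optional editorial refinement to the reporting of a non-endpoint. This conclusion rests on the visible text of section 9.4 and on analysts listing an unresolved effect as ongoing, as its recorded outcome would lead them to do. It does not rest on the simulated range, whose inputs are all assumed.

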10 SUBJECT PAYMENT

[REDACTED]

[REDACTED]

11 STUDY MANAGEMENT AND ADMINISTRATIVE PROCEDURES

11.1 Training and Monitoring

The investigators and site research staff will be trained on the study procedures. Sponsor representative(s) may be present at the site during the treatments to ensure that all procedures and documentation are in place.

Investigator will allow sponsor representatives to periodically review the study documentation. Monitoring of the site will occur at regular intervals to evaluate the progress of the study, verify the accuracy and completeness of CRFs against subject source documentation, assure that all protocol requirements, applicable FDA regulations and the investigator's obligations are being fulfilled and resolve any inconsistencies in the study records.

11.2 Informed Consent

The investigator is responsible for ensuring that written informed consent, using an Institutional Review Board (IRB) approved informed consent document, is obtained from each subject before the performance of any protocol procedures, including administration of the study device. The informed consent document must comply with all essential elements as defined in 21 CFR 50.25 "Elements of Informed Consent" and must contain a statement that consent is freely given, the study involves research, the subject is aware of the risks and benefits of entering the study, and that the subject is free to withdraw from the study at any time. An evaluation of each candidate will be conducted by the investigator. Upon determining a subject's eligibility status, the subject will be offered the opportunity to participate in the study.

The investigator or the investigator's designee will inform all subjects regarding the purpose of the study and expected duration, as well as the potential risks and benefits that may result from participation. The subjects shall be informed by the investigator or investigator's designee that they are free to refuse participation in this clinical study. If they elect to participate, it will be made clear that they may withdraw from the study at any time without prejudicing further care.

The subjects will also be informed of alternative methods of treatment should they not wish to participate in the study.

The subjects will be given the opportunity to discuss the procedure, risks, benefits, alternative therapies, and the study requirements with the investigator and have any and all questions answered to the subjects'

satisfaction. A signed and dated informed consent form must be obtained from the subject by the Investigator or the Investigator's designee prior to a subject's involvement in the study.

The acquisition of informed consent will be documented in the subject's medical records, as required by 21 CFR 812.140. A copy of the consent form will be given to the subject. The original consent forms will be kept in the CRF binder by the investigator and will be subject to review by Cutera or a representative of Cutera, and by appropriate regulatory bodies.

11.3 Protocol Compliance

The principal investigator must comply with all terms of the protocol.

11.3.1 Protocol Amendments

Neither the principal investigator nor the sponsor will modify or alter this protocol without first obtaining the concurrence of the other party (with the exception of amendments which involves mitigating a medical emergency or immediate health risk to the subject). The party initiating an amendment must confirm it clearly in writing and it must be signed and dated by the sponsor and the principal investigator. IRB approval must be obtained before implementation of an amendment.

11.3.2 Protocol Deviations

All protocol deviations must be clearly described on the case report form (i.e., Cutera Protocol Deviation Form). Deviations from the protocol may include but are not limited to subject's failure to attend scheduled visit during a visit window, use of out of range treatment parameters and incomplete or incorrect study procedures. Any medical emergency or immediate health risk to the subject which results in a protocol deviation and must be reported to the sponsor within 5 working days

Significant protocol deviations must be reported to IRB according to their policies.

11.4 Study Personnel

Prior to the start of the study, the investigator must supply the sponsor with a list of the names and curricula vitae that describe the professional backgrounds of the clinically responsible study investigators (principal, sub-investigators), research nurses, and other possible participants (e.g. medical doctor, nurse, etc.).

11.5 Disclosure of Financial Interest

Each investigator [principal and sub-investigator(s)] is required to disclose sufficient accurate financial information to the sponsor, to allow sponsor to submit complete and accurate certification or disclosure statements.

11.6 Data Collection, Record Keeping and Storage

The principal investigator is responsible for assuring that all study records including case report forms (CRFs), informed consent forms, device accountability records, source documents (e.g., medical records, histology reports etc.) and other study records are complete, accurate and recorded in a timely manner.

CRFs should not be the only record of a patient's participation in the study and will be used for transcribing data from source documents which are the point of first entry of data collected for each subject (with the exception of documents listed under B). The investigator or research staff at the site will ensure that:

A. Source documentation thoroughly and adequately documented:

1. That patient is participating in a clinical study and has been properly informed and consented prior to participation in the study,
2. Medical history,
3. Concomitant medications,
4. Patient's condition upon entering and during the course of the study,
5. Any adverse event(s) that might have occurred (in addition to the Visit CRFs and/or Adverse Device Effect CRF and/or Cutera SADE form completed),
6. Results of any diagnostic tests/histology conducted during the study.

B. The following data will be recorded directly onto CRFs:

7. Patient meets study inclusion and exclusion criteria,
8. A record of the treatment parameters, including the date of each RF treatment and any other adjunct therapy,
9. Any protocol deviations,

11. Study related improvement assessments by the investigator or investigator's designee,

C. The following documents will be maintained in the study records:

13. The Investigator or the research staff will check signed informed consent for accuracy and will always keep the original copy of the signed informed consent in the CRF binder.
14. All correspondence with an Institutional Review Board (IRB), the sponsor, or FDA including required reports will also be retained in the study records.
15. Records of receipt, use or disposition of the investigational device.

All data entries on the CRFs will be recorded completely, promptly, and legibly using blue or black indelible ink pen and accuracy will be ensured. The corrections on CRFs will be made only by the investigator or the documented investigator's designee. To make a correction to an entry, the data will be crossed through with a single line (the original entry should be visible) and then will be initialed and dated by the person making the correction.

The study records will be maintained in a secure location throughout the duration of the study. Upon study completion or termination, records will be kept at a secure location until at least 2 years after the last approval of a marketing application and until there are no pending or contemplated marketing applications or at least 2 years have elapsed since the formal discontinuation of clinical development of the investigational product.

11.7 Subject Confidentiality

This study preserves the confidentiality of all subjects under the Health Insurance Portability and Accountability Act of 1996 (HIPAA) Privacy Rule. The following safeguards will be in place to protect the privacy of the individuals who are the subjects of the health information to be used in the research and the confidentiality of that information:

The subjects will be informed by the investigator or the investigator's designee that their medical records will be kept as confidential as possible but may be subject to review by: (1) Cutera, or its representative; (2) reviewing IRB; and/or (3) by appropriate regulatory bodies (e.g. the US Food and Drug Administration (FDA), Department of Health and Human Services (DHHS) agencies).

Only pieces of personal information required for purposes of the study will be collected. The personal information will be collected and used to ensure subject eligibility for study participation, to conduct the study and to assess the results of the study as required and permitted by law. Subjects have the right to see and copy any of the information gathered about them and request changes if the information is not correct, until it is no longer kept by the investigator. Permission to use or disclose personal information, except for that has been collected and relied on may be cancelled by the subject by written notice. If the subject is withdrawn from the study, the information collected to that time may still be used to preserve the scientific integrity of the study. There is no expiration date to this authorization.

Subjects' identities will be kept confidential. Subjects will be assigned a unique study code that will not reveal the subjects' identity, and this code will be used on all study documents. To protect subject identity with regards to the photographs taken of the treatment areas, care will be taken to cover areas of photographs to protect identity. Techniques such as covering of eyes on full face photographs, cropping off portions of the face in close-up photos will be used to obscure identifying characteristics in photographs. The results of research, including photographs, may be published in scientific journals, presented at medical meetings, and used in training and marketing materials but subject identities will not be disclosed.

11.8 Publication Policy

The investigator shall have the right to publish the results of the study. Unless mutually agreed upon in writing, prior to submission for publication of any manuscript, poster, presentation, abstract or other written or oral material describing the results of the study, the investigator shall allow sponsor to review manuscript, poster presentation, abstract or other written or oral material which describes the results of the study for the purpose only of determining if any patentable information is disclosed. At the sponsor's request, the investigator shall withhold any publication or presentation to permit sponsor to seek patent protection and to remove any confidential information from all publications.

The International Committee of Medical Journal Editors (ICMJE) member journals have adopted a trials registration policy as a condition for publication. This policy requires that all clinical trials be registered in a public trials registry such as ClinicalTrials.gov, which is sponsored by the National Library of Medicine. It is the responsibility of the sponsor to register this trial in ClinicalTrials.gov. Any clinical trial starting enrollment after September 27, 2007 must be registered either on or before the onset of patient enrollment.

REFERENCES

[figure not shown]
A series of 15 horizontal black bars of varying lengths, decreasing from top to bottom. The bars are evenly spaced and extend across the width of the page.

Bar Number	Approximate Length (mm)
1	100
2	95
3	90
4	85
5	80
6	75
7	70
8	65
9	60
10	55
11	50
12	45
13	40
14	35
15	30

A bar chart illustrating the distribution of 1000 random numbers generated between 0 and 1. The x-axis represents the value of the random numbers, ranging from 0.0 to 1.0. The y-axis represents the frequency of each value, ranging from 0 to 1000. The distribution is highly skewed, with the highest frequency occurring near 0.0 and a long tail extending towards 1.0. The bars are black with thin white outlines, and the chart features a light gray background with white horizontal grid lines.

[figure not shown]
Value Range (x)	Frequency (y)
0.0 - 0.1	~950
0.1 - 0.2	~50
0.2 - 0.3	~10
0.3 - 0.4	~5
0.4 - 0.5	~2
0.5 - 0.6	~1
0.6 - 0.7	~1
0.7 - 0.8	~1
0.8 - 0.9	~1
0.9 - 1.0	~1

Appendix 3: Fitzpatrick Skin Type Classification

Appendix 4: Before and After Treatment Instructions

Before Treatment Instructions:

■ **Black**  

After Treatment Care Instructions:

Year	Publications
1990	100
1991	100
1992	100
1993	100
1994	100
1995	100
1996	100
1997	100
1998	100
1999	100
2000	100
2001	100
2002	100
2003	100
2004	100
2005	1000
2006	1000
2007	1000
2008	1000
2009	1000
2010	1000
